### 5.3 Eligibility Criteria

In order to be eligible for inclusion in the study, an individual must meet all of the following criteria:

- 30-65 years old inclusive
- Diagnosis with type 1 diabetes (T1D) or other insulin deficiency diabetes (latent autoimmune disease of adulthood, diabetes secondary to pancreatitis)
- Sedentary (<1.0 exercise sessions/wk as assessed by question #6 of Paffenbarger Physical Activity Questionnaire)
- Smartphone ownership
- English literacy
- Under regular care by a healthcare provider (defined as attending at least one appointment in the past year, plus access to verified 24hr phone number to reach the provider's team for insulin dose adjustments if assistance is needed)
- Home Broadband wireless Internet or cell phone network (≥25 mbps downloads, ≥3 mbps uploads on google Internet speed test). This is used in ~98% of US households.

•

Any individual who meets any of the following criteria will be excluded from participation in this study:

- Diabetic ketoacidosis not clearly related to pump site failure in past 6 months
- >1 episode of severe hypoglycemia (altered mental and/or physical status requiring assistance from another person for recovery) in past 6 months
- A1c ≥10.0%
- Resting blood pressure >160mmHg systolic or >100 mmHg diastolic
- Myocardial infarction or angina in past 12 months
- Uncontrolled arrhythmia (e.g., Afib with RVR, new onset Afib, ventricular tachycardia, escape rhythms)
- Congestive heart failure (stage 3 or 4)
- Exercise-induced asthma (not controlled on inhalers)

August 13, 2024

Version #7

- Chronic obstructive pulmonary disease (requiring home oxygen)
- Renal failure
- Pregnancy
- Cognitive impairment
- Severe retinopathy or neuropathy.
- Other chronic disease or physical disability that would influence exercise intervention (e.g., recent spinal surgery)

No vulnerable populations will be targeted.

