#### Mailing

After visit 1, participants will be mailed a package containing:

- a. Blood pressure monitor (Omron BP760N)
- b. CGM transmitter plus 6 sensors (Dexcom G6). If not already using. Issued by Dexcom under a research contract, not involving a prescription.
- c. Bluetooth ketone meter and test strips (Keto-Mojo GK+). The device also acts as a glucometer for CGM calibrations and sensor changes.
- d. Prepackaged snacks containing 15g fast-acting carbohydrates (e.g., Nestle Juicy Juice 125mL boxes, Glucose Tablets)
- e. Fitness smartwatch (Fitbit Inspire 3)
- f. Bluetooth Smart Insulin Pen (Companion Medical Inpen). If not a pump user. Issued by Medtronic under a research contract, not involving a prescription. A prescription for the participant's normal insulin in the correct cartridge for the InPen (3mL, U-100) will be obtained from the participant's primary diabetes care provider, or sent by a study physician through EPIC.
- g. Smartphone. If not already owned

August 13, 2024

Version #7

h. Actigraph GT9X Accelerometer. Programmed to run days 8-22, plus box to mail back so research team can download, reprogram for days 50-64, and mail to participant a second time.

In the event of lost items, up to 1 replacement will be provided, except items that are not essential for safety and have resale value (scale, fitness smartwatch, smartphone). Regardless of lost items, participants will be allowed to continue with other aspects of the study. For example, if they lose the smartwatch they can still use the exercise app with feedback missing the heart rate, steps, and sleep. Or if they lose the scale, they can still attend the weekly visits and complete the surveys and blood pressure readings. Participants will not be responsible for the cost of any lost or damaged items.

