Participants will set up the Fitbit Inspire 3 to track steps (typical ~5% overestimation) $^{92,93}$  and heart rate (typical ~3% underestimation) $^{92}$ . It will arrive to participants linked to an account set up by research staff with a generic username, generic email address, and password. Participants will be guided to place it on their non-dominant wrist and taught to mark exercise start-stop times using the side button, advised that marked bouts will have logged timing on the dashboard but all bouts are counted toward daily totals. Fitbit non-wear is defined as  $\geq$ 60 seconds without registering a pulse $^{96}$ . Participants will be instructed to wear the Fitbit at least 22 hours per day and charge it for 2 hours when the battery is low (expected every 5-7 days).

Participants will set up the Keto-Mojo GK+ which uses fingerstick strips to track blood ketones and blood glucose, the latter replacing CGM values when needed (i.e., during CGM calibrations and sensor changes). It will arrive to participants linked to an account set up by research staff with a generic username, generic email address, and password. Participants will receive a demonstration with explanation that it works like a standard glucometer, with blue strips testing ketones and brown strips testing glucose.

Participants will set up the insulin smartpen (Companion Medical InPen), over tele-video with training guided by Research Associate [name] or PI [name] (Appendix 23). It will arrive to participants linked to an account set up by research staff with a generic username, generic email address, and password. The account will be disabled for all features and alerts that guide insulin dosing and timing. The trainer will review the participant's use of their normal insulin pen, ensure they use it correctly, then orient them to the parts of the InPen so they can use it the same way as their normal pen. The trainer will also note that the InPen is reusable and train the participant to change cartridges. Patients already owning the device will be asked to use their own, or otherwise one will be provided by the research team. Patients who administer insulin in their usual care by a subcutaneous insulin infusion pump rather than multiple daily injections will continue using their

August 13, 2024

Version #7

pump and will not use a smartpen. Thus, in this study the pen introduces more comprehensive record-keeping where needed but does not alter care practices.

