# **Tracking**

A. Daily monitoring during first 2 weeks for ketoacidosis, severe hypoglycemia, and other health risks associated with exercise:

We will detect any diabetic ketoacidosis or severe hypoglycemia within 24hr and suspend exercise until a personalized preventive strategy can be formed. To achieve this level of monitoring, a research assistant will monitor daily the biometric dashboard which contains Bluetooth-captured glucose, ketones, and exercise start/stop times. Safety signals include any of the following during or within 1hr of exercise: 1) Diabetic ketoacidosis (glucose ≥270 mg/dL + ketones ≥1.0 mmol/L), 2) Possible diabetic ketoacidosis (glucose ≥270 mg/dL and failure to test ketones), and 3) Possible severe hypoglycemia (glucose <55 mg/dL). Research staff will respond to each of these events within 24hr of its occurrence by informing the participant to immediately suspend the exercise program (app account will be suspended) until the participant has been contacted by a study physician. The physician will alert the participant and the participant's primary diabetes care provider to the issue and develop a prevention strategy, consulting with the primary diabetes care provider as needed. The exercise suspension will then be lifted, unless the participant has met the protocol's stoppage criteria (>1 episode of severe hypoglycemia, 1 episode of diabetic ketoacidosis not closely related to pump site failure).

In the event of the "possible" occurrences (#2, #3), physician contact can be replaced initially by research assistant contact to query symptoms. Then, if possible diabetic ketoacidosis is supported by the participant reporting symptoms, or possible severe hypoglycemia is supported by the participant reporting altered mental and/or physical status requiring assistance from another person for recovery, physician contact will be required as in paragraph #1 above.

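### The lost-device rule in 6.1.1 calls the smartphone and smartwatch inessential to safety, yet the 8.7 daily safety review uses data they supply or probably relay, and no rule covers days when no data arrive

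*Combined protocol and SAP*

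**What the plan says.** **Lost items (6.1.1, Visit 1, Mailing).** Up to one replacement is provided, "except items that are not essential for safety and have resale value (scale, fitness smartwatch, smartphone". The next sentence reads: "Regardless of lost items, participants will be allowed to continue with other aspects of the study". The worked example for the watch is "if they lose the smartwatch they can still use the exercise app with feedback missing the heart rate, steps, and sleep". No example is given for the phone.

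**Daily safety review (8.7, Tracking, A).** Ketoacidosis and severe hypoglycemia are to be detected within 24 hr because "a research assistant will monitor daily the biometric dashboard which contains Bluetooth-captured glucose, ketones, and exercise start/stop times". The three signals share one window: "Safety signals include any of the following during or within 1hr of exercise".

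**Source of exercise times.** At Visit 2 (Devices) participants are "taught to mark exercise start-stop times using the side button" on the Fitbit, and marked bouts are logged on the dashboard. At Visit 4, Tool #2 also tracks exercise through use of the app's videos and guided walks, with Fitbit heart rate as verification.

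**Daily diaries and surveys.** Section 2.2 has the team learn of severe events within 24 hr through daily diaries. Section 8.7 picks up other exercise-related health risks from the morning survey.

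**Who has a phone.** Section 5.3 lists "Smartphone ownership" as an inclusion criterion. Item g of the mailed package is "Smartphone. If not already owned".

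**The concern.** The lost-item rule and the safety plan classify the same devices differently. One treats them as dispensable and lets the participant carry on. The other rests its 24-hr detection on data that one device produces (exercise times) and the other probably relays (glucose, ketones, survey answers).

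Section 2.2 rates the study as greater than minimal risk and cites the protocol's protective measures in weighing that risk; the daily review is one of them. The protocol also treats one kind of missing safety data as a reason to act: a missed ketone test suspends exercise until the participant has been contacted. It has no counterpart for a feed that goes silent altogether.

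The smartphone mismatch is separate and needs no inference. As written, a screener cannot tell whether a non-owner is eligible.

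**Working it through.** No figure in the plan is at issue, so the check sets passages side by side: list what each 8.7 signal needs, then remove one device at a time.

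**Inputs per signal (8.7, Tracking, A)**

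| Signal | Glucose | Ketones | Exercise time |
|---|---|---|---|
| 1. Ketoacidosis | ≥270 mg/dL | ≥1.0 mmol/L | yes |
| 2. Possible ketoacidosis | ≥270 mg/dL | test absent | yes |
| 3. Possible severe hypoglycemia | <55 mg/dL | not needed | yes |

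**Watch lost.** Glucose and ketones do not come from the Fitbit (Table A1). App usage still times video and guided-walk sessions (Tool #2).
- App sessions: 3 of 3 signals evaluable, without heart-rate verification of timing.
- Exercise outside the app: 0 of 3 signals can be tied to exercise, because the marked times are gone.

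**Study-supplied phone lost.** Three places point to the phone as the relay:
- The synopsis (Online locations) says the GlucoseZone mobile app captures Dexcom and Fitbit data.
- Section 2.2 says data are deleted from biosensors and smartphones after syncing.
- Item b of the mailed package lists a transmitter and sensors but no receiver.

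Table A1 shows only manufacturer-to-GlucoseZone links for CGM and a researcher dashboard for the ketone meter; it names no phone. If the phone is the relay, 0 of 3 signals are evaluable. The app and the morning survey are also unavailable on that phone.

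**Does absent data trigger anything?** Signal 2 covers a missing ketone test, but only after a glucose of at least 270 mg/dL has been received. With no glucose received, none of the three signals can fire.

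**Would staff notice?** Section 7.6 has diaries monitored daily, and Tool #2 has staff at the dashboard daily. A gap should therefore show within about a day. Neither passage ties an action on exercise to it.

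**Length of exposure per loss**
- Sections 2.2 and 8.7 state daily review for the first 14 days. Maximum = 14 days. Mean for a loss uniformly distributed within that window = 14/2 = 7 days. This assumes the window falls while the participant is exercising; the documents do not say from which visit it is counted.
- Tool #2 implies daily dashboard use throughout the 4-week intervention. On that reading the maximum = 28 days and the mean = 28/2 = 14 days.

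**Number affected.** The documents give no loss rate and no count of study-supplied phones. If 5.3 is enforced, that count should be close to zero; if item g prevails, it is unknown.

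**The case against.** The strongest reply is that the gap is small and partly closed by other provisions.

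- Continuation is allowed only for other aspects of the study. The exercise program is a mobile app, so losing the phone also stops app-guided exercise. This stands in part: nothing addresses exercise outside the app, and the continuation sentence makes no exception for the phone.
- The phone as sole relay is inferred, and existing CGM users may have other equipment. This stands, and the conclusion is worded accordingly.
- Other protections survive phone loss: a replaceable fingerstick glucose and ketone meter, the safety orientation, weekly symptom checks, direct contact with the principal investigator, and emergency access. This also stands. The 24-hr review is retrospective and is not the only safeguard.
- Few people hold a study phone, and the rule may not reach a participant's own phone. This limits the numbers but does not remove the conflict in wording.

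Three stronger readings are tempting and should not be drawn:

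1. A reader might infer that losing either device leaves none of the signals evaluable. That fits the phone only, and by inference; with the watch lost, all three remain for app sessions.
2. A reader might infer that a gap would surface only at the two-weekly CGM audit. The daily diary and dashboard checks contradict that.
3. A reader might count exposure through follow-up (28 + 14 = 42 days). App use ends at Visit 8, and no passage describes daily glucose and ketone review in follow-up.

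**Conclusion.** The conflict is real and should be corrected, but its reach is modest. The inessential-to-safety label cannot stand beside an 8.7 review that uses these devices' data, and the plan is silent on what follows when the feed stops.

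For the phone, the consequence is probable loss of all three signals, the app and the daily survey until a relay is restored. This rests on the inferred data path. For the watch, the consequence is limited to lost times for exercise outside the app and unverified times within it.

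Exposure per phone loss is at most 14 days on the stated review period, or 28 if review is daily throughout the intervention. How many participants are affected cannot be estimated from the documents and is probably few. The eligibility contradiction over smartphone ownership holds without any assumption.

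**What to change.** 1. In 6.1.1 (Mailing), take the smartphone out of the exception so that the existing one-replacement rule covers it. Cost: at most one phone per loss.
2. For the smartwatch, either do the same (at most one watch per loss) or state in 8.7 that app session logs supply the exercise times when the watch is missing (wording only).
3. Reconcile the continuation sentence in 6.1.1 with 8.7 for days when no data arrive. The rule on exercise during such days is for the study physicians to set; none is proposed here. Cost: one decision and a short insertion.
4. Reconcile 5.3 with item g of the mailed package, so that screeners know whether non-owners are eligible. Cost: wording only.

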## VISIT 2 (Day 8)

#### **Devices**

Participants not currently using a Dexcom G6 CGM will be trained over tele-video by Research Associate [name] or PI [name]. The training protocol incorporates information from the manufacturer setup protocol plus additional guidance provided by the study endocrinologists Drs. [name] and [name] (Appendix 21). Participants will log into either their own Dexcom account (current users) or an anonymous account set up by research staff with a generic username, generic email address, and password (new users) and pair the device. They will be guided to create a "share code" that gives the holder access to CGM data in real-time; research staff will record the code on Yale's secure server for transmission to their primary diabetes care provider. The CGM is validated against venous blood glucose (mean absolute percentage error 9%-10%86,91). For the 2-week familiarization period until visit 4, the trainer will review CGM data after days 1, 3, 7, 10, and 14 days to check if data are being transmitted consistently with reasonable values and if the first sensor change (day 10) was completed as scheduled). The trainer will also talk with the participant at each weekly visit and query if there are any issues with skin irritation, sensor dislodgement, or values suspicious or inconsistent with fingerstick checks. At the visit 2 weeks after initiation (visit 4), they will ask if there were any issues with the first sensor change. Trainer will follow up with participant to troubleshoot as needed. We will start with a bank of standard troubleshooting techniques from our procedure manual, then involve Dexcom customer service or a senior clinician from the research team as needed.

Participants will set up the Fitbit Inspire 3 to track steps (typical ~5% overestimation) $^{92,93}$  and heart rate (typical ~3% underestimation) $^{92}$ . It will arrive to participants linked to an account set up by research staff with a generic username, generic email address, and password. Participants will be guided to place it on their non-dominant wrist and taught to mark exercise start-stop times using the side button, advised that marked bouts will have logged timing on the dashboard but all bouts are counted toward daily totals. Fitbit non-wear is defined as  $\geq$ 60 seconds without registering a pulse $^{96}$ . Participants will be instructed to wear the Fitbit at least 22 hours per day and charge it for 2 hours when the battery is low (expected every 5-7 days).

Participants will set up the Keto-Mojo GK+ which uses fingerstick strips to track blood ketones and blood glucose, the latter replacing CGM values when needed (i.e., during CGM calibrations and sensor changes). It will arrive to participants linked to an account set up by research staff with a generic username, generic email address, and password. Participants will receive a demonstration with explanation that it works like a standard glucometer, with blue strips testing ketones and brown strips testing glucose.

Participants will set up the insulin smartpen (Companion Medical InPen), over tele-video with training guided by Research Associate [name] or PI [name] (Appendix 23). It will arrive to participants linked to an account set up by research staff with a generic username, generic email address, and password. The account will be disabled for all features and alerts that guide insulin dosing and timing. The trainer will review the participant's use of their normal insulin pen, ensure they use it correctly, then orient them to the parts of the InPen so they can use it the same way as their normal pen. The trainer will also note that the InPen is reusable and train the participant to change cartridges. Patients already owning the device will be asked to use their own, or otherwise one will be provided by the research team. Patients who administer insulin in their usual care by a subcutaneous insulin infusion pump rather than multiple daily injections will continue using their

August 13, 2024

Version #7

pump and will not use a smartpen. Thus, in this study the pen introduces more comprehensive record-keeping where needed but does not alter care practices.

For the 2-week familiarization period until visit 4, the trainer will review InPen data after days 1, 3, 7, 10, and 14 days to check if data are being transmitted consistently with reasonable values. The trainer will also talk with the participant at each visit and query of there are any issues or concerns. Trainer will follow up with participant to troubleshoot as needed. We will start with a bank of standard troubleshooting techniques from our procedure manual, then involve Medtronic customer service or a senior clinician from the research team as needed.

Participants will set up the Actigraph GT9X hip accelerometer (i.e., blinded hip and wrist watch) on their own belt, elastic waistband, or a belt we provide. They are asked to wear the device on the hip for all waking hours except bathing, and on the dominant wrist (i.e., opposite wrist of the Fitbit) for sleep. The device samples data at 30Hz and aggregates it into 60-second epochs. Non-wear periods are defined by Troiano's algorithm^94 confirmed against participant logs of non-wear periods; previously our wear time exceeded literature standards (14.1±1.9 waking hours per day for 5.4±1.0 out of 7 days). Participants will receive a daily morning SMS survey through Ilumivu or Qualtrics asking them to log that morning's attachment time and previous night's removal time.

Participants will measure blood pressure by standard home monitoring procedures. We will take the average of 2 brachial artery measurements after ≥12 hours abstention from acute blood pressure confounders (exercise, caffeine, alcohol, tobacco, nicotine) and ≥5 minutes of quiet rest using the Omron BP760N, which includes a rigid cuff that minimizes fitting errors. If the measurements differ by >5 mmHg, then a third will be taken and the closest two will be averaged. In the event of a result meeting the home BP monitoring criteria for uncontrolled accelerated hypertension (systolic >160 mmHg and/or diastolic >100 mmHg), the participant will be withheld from exercise participation until BP can be reassessed at least one day later. In the event of a second occasion meeting these values, the participant will be removed from the study and referred to their healthcare provider for follow-up.

Daily morning survey that captures daily morning context during app intervention is started at this visit -- Appendix 8a: 1) prior day hypoglycemia episodes; 2) recent clinical events (asked every day for 2 weeks, then every 2 weeks); 3) fear of hypoglycemia previous night and coming day; 4) sleep quality and nocturia previous night; 5) competing demands and exercise plan for the day.

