Participants will be monitored for exercise-associated events (hypo- and hyperglycemia, diabetic ketoacidosis, other health risks) as detailed in the Data and Safety Monitoring Plan (Sect 8.7). In brief, a research staff member will daily review each participant's CGM data, fingerstick glucose tests, ketone tests, exercise start times, and diary records of hypoglycemia and other clinical events (see Data and Safety Monitoring Plan "Tracking" section) each of the first 14 days of the trial for each participant. Instances of severe hypoglycemia, diabetic ketoacidosis, a missed ketone test, or other clinical event will result in immediate discontinuation of exercise until a physician has alerted the participant and the participant's primary diabetes care provider to the issue and developed a prevention strategy, consulting with the primary diabetes care provider as needed. For instances of a missed test, physician contact can be replaced initially by research assistant contact to query symptoms and troubleshoot testing procedures, followed by physician contact if symptoms were present.

The principal investigator [name] and a study physician (Drs. [name] or [name]) will review the above data plus carbohydrate and insulin dosing around exercise, every 2 weeks during the clinical trial. Participants exhibiting patterns confirmed by the physician to be indicative of problematic exercise-induced hypo- or hyperglycemia will be alerted to the issue and referred to their diabetes care provider for follow-up (all patients will submit provider information to the study team at study start). [name] will join at least every other occurrence of these meetings (i.e., at least every 4 weeks) and provide a second review of [name] medical management decisions. Participants will be trained in allowing their provider to access their CGM data. Mild hypoglycemia will not be exclusionary since such individuals are in high need of exercise intervention. Any day-to-day decisions about clinical care, including adjustment of insulin dosing or CGM target ranges will be made by the participant's provider, not the study physicians. Clinical providers will not monitor CGM in real-time.

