# **Start of Intervention**

Participants will download and be oriented to use the GlucoseZone™ (New Haven, CT) mobile application that delivers the digital intervention. The intervention is designed to target 150 minutes of weekly exercise, in accord with recommendations. Participants utilize exercise videos with biometrically-driven feedback coaching.

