#### Data Captured by App

**Daily context each morning -- Appendix 8a:** 1) prior day hypoglycemia episodes; 2) recent clinical events (asked every 2 weeks only); 3) fear of hypoglycemia previous night and coming day; 4) sleep quality and nocturia previous night; 5) competing demands and exercise plan for the day.

Pre- and mid-exercise context captured in conjunction with videos – Appendix 8b & 8c and passive data from app and sensors:  $\underline{1}$ ) carbohydrates taken;  $\underline{2}$ ) insulin dosing;  $\underline{3}$ ) weather;  $\underline{4}$ ) day of the week;  $\underline{5}$ ) exercise instructional video selected; 6) exercise performance metrics.

**24hr passive data from sensors –** 1) Continuous blood glucose; 2) Physical activity outside of exercise videos

The app uses this biometric data to give exercise guidance, as described in the funded grant submission (1K01DK129441) and below

Tool #1: Access to a library of 200 exercise videos following brief human orientation consultation (Appendix 18b). Our ~200 exercise videos (GlucoseZone™, New Haven, CT) include a combination of aerobic, resistance, flexibility, and balance exercises, in accord with American Diabetes Association recommendations. They can be filtered by difficulty level, duration, type of exercise (aerobic vs. resistance), muscle groups, mobility limitations (knee-friendly, shoulder-friendly, chair-based), indoor/outdoor, and home equipment availability. Using these filters, participants can select single sessions or 30-session series that progress in difficulty and duration. Participants self-schedule exercise time in their home environment or outdoor guided walking routes. Participants may select routines requiring no equipment, use a \$10 set of resistance bands we recommend, use their dumbbells or household items like frozen water bottles. A trained exercise physiologist (EP) from the research team ([name],) will guide downloading the app, discuss exercise levels, goals and safety (Appendix 22a), and recommend starting videos and series. This orientation will be audio-recorded and combined with later interviews for qualitative analysis (Sect 7.2.1, hypothesis 2-3). A consultant from the manufacturer of GlucoseZone (Fitscript LLC; [name] [name] or [name]) will be available for assistance with downloading, navigating, or troubleshooting the app.

August 13, 2024

Version #7

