We will detect any other exercise-associated health risks within 24-36hr and suspend exercise until a personalized preventive strategy can be formed. To achieve this level of monitoring, the morning survey question about prior day's clinical events (Appendix 8a, last question) will be asked of participants and monitored by research staff daily. If the participant reports a clinical event, the PI will complete Adverse Event review and summary (c.f. Protocol Sect 6.3) the same day (i.e., within 24-36hr of the reported event). If the event may be exercise-related, the participant will be informed to immediately suspend the exercise program (app account will be suspended) until the participant has been contacted by a study physician. The physician will alert the participant to the issue and develop a prevention strategy, consulting with the participant's primary diabetes care provider as needed. The exercise suspension will then be lifted, unless the participant has met the protocol's stoppage criteria.

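### Section 8.7 withholds exercise at a diastolic limit that the rest of the plan contradicts, and the two daily weeks of the clinical-event question end before app exercise begins

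*Combined protocol and SAP*

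**What the plan says.** **Blood pressure.** Section 8.7, Tracking, part C, describes earlier trials that used limits of 160 mmHg systolic and/or 100 mmHg diastolic and says these will be used here. Its procedures then set two tiers. A reading above 145 and/or 90 is faxed to the diabetes provider. A reading above 160 and/or 90 withholds the participant from exercise, and a second such occasion leads to removal. Section 6.1.1 (Visit 2) describes the same withholding and removal at 160 and/or 100. Section 5.3, section 6.5 and the screening criteria in 8.7 (Exercise-related injuries) also use 160 and 100.

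**Clinical-event question.** Section 8.7, Tracking, part A, commits the team: "We will detect any other exercise-associated health risks within 24-36hr and suspend exercise until a personalized preventive strategy can be formed". The stated means is that "the morning survey question about prior day's clinical events (Appendix 8a, last question) will be asked of participants and monitored by research staff daily", and a possibly exercise-related event leads to suspension of the app account. The heading over this text is "Daily monitoring during first 2 weeks for ketoacidosis, severe hypoglycemia, and other" health risks. It gives no starting day. Section 2.2 places daily staff review on "each of the first 14 days of the trial for each participant".

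The visit procedures give the schedule. At Visit 2 (Day 8), "Daily morning survey that captures daily morning context during app intervention is started at this visit", and it includes "recent clinical events (asked every day for 2 weeks, then every 2 weeks". At Visit 4 (Day 22), "Participants will download and be oriented to use the GlucoseZone" app, and the survey from then on has "recent clinical events (asked every 2 weeks only".

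**The concern.** Each rule tells staff when to stop a participant exercising, and each can be read two ways.

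For blood pressure, an eligible participant with a diastolic between the two limits is withheld and then removed under section 8.7, but continues under section 6.1.1. The lower figure errs toward caution. It also makes the diastolic limit of the withhold tier the same as that of the fax-only tier, so on the diastolic side the early warning no longer comes before anything.

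For the survey, the two weeks of daily asking are tied to the device run-in. The participants are sedentary at entry, and app exercise begins only when run-in ends. A non-glycemic event in the first two weeks of that exercise, such as a muscle strain, has no daily prompt to bring it to staff. The app suspension in section 8.7 then waits for the next scheduled contact, unless the participant calls first.

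**Working it through.** The plan states no figure to reproduce. The check compares the texts and counts days.

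**Blood pressure limits**

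| Place | Purpose | Systolic | Diastolic |
|---|---|---|---|
| 5.3 | Exclusion | >160 | >100 |
| 6.1.1, Visit 2 | Withhold, then remove | >160 | >100 |
| 6.5 | Individual stopping criterion | >160 | >100 |
| 8.7, Exercise-related injuries | Exclusion | >160 | >100 |
| 8.7, Tracking C, limits adopted | Stated basis | >160 | >100 |
| 8.7, Tracking C, alert | Fax only | >145 | >90 |
| 8.7, Tracking C, action | Withhold, then remove | >160 | **>90** |

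Only the last row departs from 100 for an exclusion or stopping decision. In whole mmHg the affected band is diastolic 91 to 100 with systolic at or below 160. Visits 2 to 10 give 9 scheduled readings at which it can arise.

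**Overlap of daily asking with app exercise (nominal visit days)**

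- Daily item: starts Day 8 and runs 14 days, so Days 8 to 21.
- First 14 days of app exercise: from Day 22, so Days 22 to 35.
- Overlap: 0 of 14 days.

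Visits have a window of ±7 days. With Visit 2 on Day 8 and Visit 4 as early as Day 15, the Visit 2 text alone would give Days 15 to 21, or 7 of 14. The Visit 4 text still makes the item 2-weekly once the app starts.

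**Scheduled lag to staff for events on Days 22 to 35**

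The scheduled contacts are the weekly checks at Visits 5 and 6 (Days 29 and 36) and one 2-weekly ask at about Day 35 (Day 21 + 14). An event on a visit day is taken to follow that visit, the 2-weekly ask is taken to pick up any event since the last contact, and no participant is assumed to call in.

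- Events on Days 22 to 28 surface on Day 29: lags 7, 6, 5, 4, 3, 2, 1, sum 28.
- Events on Days 29 to 34 surface on Day 35: lags 6, 5, 4, 3, 2, 1, sum 21.
- An event on Day 35 surfaces on Day 36: lag 1.
- Mean: (28 + 21 + 1) / 14 = 50 / 14 = 3.57 days, and 3.57 × 24 is about 86 hours.
- Against the target: 86 / 36 = 2.4 and 86 / 24 = 3.6 times.
- Lags of 2 days or more, which exceed 36 hours: 6 (Days 22 to 27) + 5 (Days 29 to 33) = 11 of 14 days.

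If the Day 35 ask is left out, both weeks sum to 28. The mean is then 56 / 14 = 4.0 days, with 12 of 14 days over 36 hours. The conclusion does not turn on that ask.

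**The case against.** The best reply on the survey is that the documents agree on one pattern, two weeks daily and then 2-weekly. The heading in 8.7 limits daily monitoring to two weeks, section 2.2 counts them from the start of the trial, and the Visit 2 text matches. This stands as far as it goes. A reader might infer that 8.7 promises daily asking throughout and that the visit procedures break that promise. The heading rules this out, and only the start point is at issue. On the start point, the 8.7 text concerns exercise-associated events and suspension of an app account that does not exist before Visit 4.

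It would also be too much to say that nothing about exercise can be monitored before Visit 4, because participants learn at Visit 2 to mark exercise start and stop times on the Fitbit. Nor is staff review absent during the intervention. Tool #2 in section 6.1.1 describes a daily dashboard check, and section 7.6 has diaries monitored daily. But daily review cannot show an answer to a question not asked that day.

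Other safeguards narrow the harm. The safety orientation covers symptoms to watch for and whom to call with concerns. Participants have the principal investigator's direct contact details. They are told to use the 24-hour line or 911 after severe events and to contact their provider if pain persists. Severe glycemic events are to reach the team within 24 hours through the diaries. What remains is prompt, prompted capture of non-glycemic events, chiefly those the participant does not think severe enough to report.

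Appendix 8a was not available. Section 8.7 calls the item the appendix's last question, about the prior day. The visit procedures list recent clinical events second of five topics. They are probably the same item, and the appendix could set the schedule used in practice.

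On blood pressure, the intent can be recovered from 8.7 itself, the slip is cautious, removal there needs a second occasion, and withdrawal under 6.5 is discretionary. A reader might infer a material loss from the 24 participants. The documents give no distribution of diastolic pressure, so they do not support a number.

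**Conclusion.** Both points hold and should be corrected. Neither touches the analyses of the objectives.

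The diastolic limit of 90 for withholding and removal is an error on the documents' own terms, since the same section adopts 100 and every other stopping or exclusion rule uses 100. Its reach is the 91 to 100 band, and the number of participants affected cannot be estimated.

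The daily clinical-event question is anchored to the wrong start. As written it nominally covers 0 of the first 14 days of app exercise. The scheduled lag averages about 3.6 days (86 hours, 2.4 to 3.6 times the target) and exceeds 36 hours for events on 11 of those 14 days. These figures rest on nominal visit days, one 2-weekly ask near Day 35, no participant-initiated contact, and the two descriptions of the question meaning the same item. The conclusion concerns the timing of scheduled capture. It does not mean that participants lack a way to report events, or that daily asking was promised beyond two weeks.

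**What to change.** 1. Section 8.7, Tracking, part C: change the withhold and remove limit to diastolic above 100 mmHg. Keep 145 and/or 90 as the fax-only alert.
2. Section 6.1.1, the morning-survey text at Visit 2 and the Data Captured by App text at Visit 4: ask the clinical-event item daily for the first 2 weeks after Visit 4, then every 2 weeks. Daily asking during familiarization as well is optional.
3. Section 2.2 and the heading of section 8.7, Tracking, part A: count the 14 days from Visit 4.
4. Check that Appendix 8a carries the same schedule.

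The cost is amendment wording, plus at most 24 × 14 = 336 extra one-item prompts across the study, in a survey already sent every day. If the daily period is moved and not extended, there are no extra prompts.
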